# **10.7.** Regulatory Aspects of Adverse Event Reporting

The Sponsor is responsible for submitting reports of SAEs associated with the use of the study drug to the appropriate Regulatory Authority (e.g., the US Food and Drug Administration), Investigators, and IRB/IEC/central ethics committee (CEC) in accordance with all applicable regulations and guidelines.

It is the responsibility of the Investigator to notify the IRB of all SAEs that occur at his or her site. Investigators will be notified of all suspected unexpected serious adverse reactions (SUSARs; 7 / 15 Day Safety Reports) that occur during any clinical studies that are using the investigative compound. Each site is responsible for notifying their IRB/IEC/CEC of these additional SUSARs in accordance with local regulations.

#### 10.8. Overdose

In the case of overdose, clinic staff should be notified immediately, and supportive care is to be given as indicated. Patients should be informed to contact their doctor immediately if they have taken an overdose and should stop taking duvelisib.

For this study, overdose is defined as a daily dose of duvelisib higher than the prescribed daily dose. Overdoses will not be considered SAEs unless the outcome of the overdose meets seriousness criteria as defined in Section 10.2, Definition of a Serious Adverse Event. In the event of an overdose, the Sponsor should be immediately notified. The patient should be carefully monitored for potential adverse reactions and symptomatic treatment instituted as per institutional standards of care.

# 10.9. Pregnancy

Pregnancy per se is not considered an AE unless there is cause to believe that the study drug may have interfered with the effectiveness of a contraceptive medication or if the outcome of the pregnancy meets SAE criteria (miscarriage or congenital anomaly/birth defect, etc.), in which case it should be reported in the same manner and timelines as an SAE. In addition, any infant death or congenital anomaly occurring after 30 days that the Investigator suspects is related to the in-utero exposure to the study drug should also be reported as an SAE. Hospitalization for normal delivery of a healthy newborn is not an SAE.

Since duvelisib has not been evaluated in pregnant or nursing women, the treatment of pregnant women or WCBP who are not using effective contraception is contraindicated (see Section 6.10.2 and Section 9.5.3 for instructions on pregnancy testing and birth control).

Pregnancies occurring in patients or partners of male patients during the study treatment period until 30 days after the patient's last dose of study treatment are considered immediately reportable events. If a pregnancy occurs in a patient, study treatment must be discontinued immediately. The pregnant woman should be referred to an obstetrician/gynecologist experienced in reproductive toxicity for further evaluation and counseling.

The pregnancy must be reported to the Sponsor or designee within 24 hours of the Investigator's knowledge of the pregnancy using a Pregnancy Report Form.

The Investigator will follow the pregnant woman until completion of the pregnancy and must notify the Sponsor of the outcome within 24 hours of the Investigator's knowledge of the pregnancy outcome using a Pregnancy Outcome Form. This notification includes pregnancies resulting in live, "normal" births.

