# 1.4. Benefit/Risk Assessment

Clinical study results to date support a favorable benefit-risk of duvelisib for patients with hematologic malignancies. The risks are consistent with the AE profile for the PI3K inhibitor drug class and AEs experienced by patients undergoing treatment for advanced cancers. Important identified risks include infections, diarrhea/colitis, cutaneous reactions, pneumonitis, neutropenia, and ALT/AST elevation. Potential risks include hepatotoxicity, drug-drug interaction (DDI) and reproductive toxicity. These toxicities are managed using a combination of prophylaxis, supportive care and dose modifications. Duvelisib monotherapy has demonstrated encouraging activity in relapsed and refractory PTCL seen in this study and the Phase 1 study in hematologic malignancies. The starting dosage will be 75 mg BID until the first response assessment (2 cycles) in an attempt to debulk the tumor more efficiently. Subsequently, the dose will be reduced to 25 mg BID to anticipate and reduce toxicities of later times of onset. As both dose levels have demonstrated preliminary responses, this strategy is designed to reduce the risk of toxicity while maintaining clinical benefit. Overall, the potential benefit to a patient

with relapsed/refractory PTCL with few treatment options and historically a dismal prognosis, appears at this time, to outweigh any potential risks.

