- 11. Male and female patients of reproductive potential (i.e., not surgically sterile or female patients who are not postmenopausal) must be willing to use a highly effective method of contraception for the duration of study treatment and for at least 3 months after the last dose of duvelisib
- 12. Signed and dated institutional review board (IRB)/independent ethics committee (IEC)/central ethics committee (CEC)-approved informed consent form before any Screening procedures are performed

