# 14. **APPENDICES**

#### APPENDIX 1: CONTRACEPTION GUIDANCE

The effects of duvelisib on conception, pregnancy, and lactation are unknown. Every woman of childbearing potential (WCBP) and male patients with a partner who is a WCBP must use contraception as described below. A woman is considered to be a WCBP after menarche and until becoming postmenopausal (i.e., > 55 years and postmenopausal for at least 1 year), unless permanently sterile.

At Screening, all male and female patients of reproductive potential (i.e., not surgically sterile or female patients who are not postmenopausal) must agree to use a highly effective method of contraception (see below) for the duration of study treatment, and for at least 3 months after the last dose of duvelisib. Male patients must also refrain from donating sperm during their participation in the study and for at least 3 months after the last dose of duvelisib.

The use of contraceptive methods is not required if the male patient or the male partner (of the female patient) has a documented history of a vasectomy or if the female patient or the female partner (of the male patient) has a documented history of bilateral oophorectomy, hysterectomy, or tubal ligation, or if she is > 55 years of age and postmenopausal for at least 1 year.

See Section 10.9 for requirements for pregnancy reporting.

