#### **Highly Effective Forms of Contraception**

Methods that can achieve a failure rate of less than 1% per year when used consistently and correctly are considered as highly effective birth control methods. Such methods include:

- combined (estrogen and progestogen containing) hormonal contraception associated with inhibition of ovulationa:
  - oral
  - intravaginal
  - transdermal
- progestogen-only hormonal contraception associated with inhibition of ovulationa:
  - oral
  - injectable
  - implantableb
- intrauterine device (IUD)b
- intrauterine hormone-releasing system (IUS)b
- bilateral tubal occlusionb
- vasectomized partnerb,c
- sexual abstinenced

a Hormonal contraception may be susceptible to interaction with the IMP, which may reduce the efficacy of the contraception method.

bThis method of contraception should preferably be used, in particular when contraception is introduced as a result of participation in the clinical study.

cVasectomized partner is a highly effective birth control method provided that partner is the sole sexual partner of the WCBP study participant and that the vasectomized partner has received medical assessment of the surgical success.

d Sexual abstinence is considered a highly effective method only if defined as refraining from heterosexual intercourse during the entire period of risk associated with the study treatments. The reliability of sexual abstinence needs to be evaluated in relation to the duration of the clinical study and the preferred and usual lifestyle of the patient.

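### Routine pregnancy reporting ends 30 days after the last dose while contraception is required for at least 3 months, so a pregnancy beginning in the roughly 60 days between is captured only if a separate exception applies

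*Protocol*

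**What the plan says.** **Reporting (Protocol Section 10.9).** The events that must be reported at once are "Pregnancies occurring in patients or partners of male patients during the study treatment period until 30 days after" the patient's last dose. The sponsor is to be told within 24 hours on a Pregnancy Report Form. The investigator follows the woman to the end of the pregnancy and sends an outcome form, which is also expected for normal live births.

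**Contraception.** Inclusion criterion 11 (Section 5.1) requires highly effective contraception "for the duration of study treatment and for at least 3 months after the last dose of duvelisib". Section 9.5.3 and Appendix 1 give the same period. Appendix 1 adds: "Male patients must also refrain from donating sperm during their participation in the study and for at least 3 months after the last dose".

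**Why precaution is asked for.** Section 1.4 states: "Potential risks include hepatotoxicity, drug-drug interaction (DDI) and reproductive toxicity". Section 9.5.3 and Appendix 1 say that the effects on conception, pregnancy and lactation are not known.

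**Exceptions that can reach later cases.** Section 10.9 treats a pregnancy as an AE if the study drug may have weakened a contraceptive, or "if the outcome of the pregnancy meets SAE criteria (miscarriage or congenital anomaly/birth defect, etc.), in which case it should be reported" like an SAE. It also asks for infant death or congenital anomaly after 30 days to be reported as an SAE where the investigator suspects in-utero exposure. Section 10.3 requires any SAE after the reporting period to be reported if a causal link to the drug is suspected.

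**Testing and analysis.** In Protocol Tables 1 and 2 the last scheduled pregnancy test is at the Safety Follow-up visit, 30 + 7 days after the last dose. SAP Section 5.3.9 plans only a by-patient listing of pregnancy test results.

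**The concern.** The protocol asks patients to avoid conception for at least 3 months after stopping the drug, but stops asking about failures after one. It gives no reason for the difference.

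For a pregnancy that begins after day 30 and inside the contraception period, nothing clearly requires the report form, follow-up or the outcome form. At stake is information on a risk that the protocol itself names, and the follow-up of a woman and infant. There is also a problem of interpretation. The routes that remain select mainly for adverse outcomes or a suspected drug link. A sponsor that collects mostly the bad outcomes from this period has no denominator against which to read them. Section 10.9 wants normal births reported inside its window, so the sponsor evidently sees the value of a denominator.

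**Working it through.** The documents give no statistical figure to reproduce. The check sets the windows side by side and subtracts dates.

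**Inputs**

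| Item | Period after last dose | Source (Protocol) |
|---|---|---|
| Routine pregnancy reporting, patients and partners | 30 days | Section 10.9 |
| Contraception | at least 3 months | Criterion 11; Section 9.5.3; Appendix 1 |
| No sperm donation | at least 3 months | Appendix 1 |
| Last scheduled pregnancy test | day 30 to day 37 | Tables 1 and 2 |

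**Step 1: length of the gap.** Three calendar months run from 89 to 92 days, depending on the months.

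- Shortest: 89 − 30 = 59 days; 59/89 = 66%.
- Longest: 92 − 30 = 62 days; 62/92 = 67%.

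So about 60 days, or two thirds of the minimum post-treatment contraception period, lie outside the reporting window. This is a ratio of calendar days, not a forecast of events, and it leaves out the treatment period, which is fully covered.

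**Step 2: days without a scheduled test.** If the Safety Follow-up visit falls on its latest day, 89 − 37 = 52 to 92 − 37 = 55 days of the contraception period have no scheduled test. Partners are not tested at any time.

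**Step 3: what happens to a pregnancy that begins in the gap.**

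| Case | Route | Captured? |
|---|---|---|
| Drug suspected of weakening a contraceptive | Section 10.9, exception to the non-AE rule | Yes, if the link is suspected and the site knows |
| Miscarriage, congenital anomaly or other outcome meeting SAE criteria | Section 10.9; that sentence carries no 30-day limit | Yes, if the site learns of it |
| Infant death or anomaly suspected to come from in-utero exposure | Section 10.9 | Yes, if the site learns of it and suspects a link |
| Other late SAE suspected to be related | Section 10.3 | Yes, if the site learns of it and suspects a link |
| Uncomplicated pregnancy or normal birth, no suspected interference | None clearly required | No |

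Each route that works assumes that the investigator hears about a pregnancy that no one has been asked to report. This is weakest for partners, who have no study visits.

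**Step 4: is 3 months the protocol's risk window?** The nearest wording is in the Appendix 1 footnote on abstinence: "refraining from heterosexual intercourse during the entire period of risk associated with the study treatments". No length is attached to it. The only post-treatment length in the contraception rules is 3 months. Reading that as the protocol's precautionary window is reasonable, but it is an inference.

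**The case against.** Prevention and reporting windows serve different purposes, and both can be followed as written. The 30-day limit matches the general AE and SAE reporting period in Sections 7.3 and 10.3, and testing runs through the Safety Follow-up visit. A contraception rule may carry a deliberate safety margin. This much stands: the protocol does not instruct two incompatible things. It leaves a gap without giving a reason.

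Three stronger readings are tempting, and the documents do not support them.

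- **That pregnancies in the gap are neither reported nor followed.** Sections 10.9 and 10.3 keep four routes open, and the one for outcomes meeting SAE criteria has no 30-day limit in its sentence. The routes are incomplete, not absent.
- **That the protocol declares 3 months to be the exposure-risk period.** No section says so; see step 4 of the working.
- **That data on drug-exposed pregnancies are being discarded.** The documents give no half-life or washout basis showing that a conception on days 31 to 90 is exposed to the drug.

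On frequency the objection is also fair. Section 1.1 says that the disease generally affects people aged 60 and older, so few pregnancies are likely. The number is not zero by design, because enrolment is open from age 18 and partners of male patients are covered.

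**Conclusion.** The concern holds in a limited form. Routine reporting and follow-up to outcome stop at 30 days, while the protocol requires precautions for at least 3 months. In the 59 to 62 days between, an uncomplicated pregnancy with no suspected interference triggers no reporting duty even when the plan is followed exactly. Adverse or suspect cases are reported only if the site happens to learn of them.

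The conclusion rests on three assumptions:

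- A pregnancy counts as occurring when it begins. One that begins by day 30 and is recognised later is taken to be inside the window.
- The follow-up and outcome-form duties in Section 10.9 apply to the pregnancies that the section makes reportable.
- The contraception period reflects a precaution about conception after treatment.

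This is a low-frequency gap in safety capture for a named potential risk. It affects no endpoint, sample size or efficacy analysis. It merits correction because correction is cheap, not because many cases are expected.

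**What to change.** 1. Reconcile Section 10.9 with criterion 11, Section 9.5.3 and Appendix 1. Extend the window for pregnancy reporting and follow-up to outcome, for patients and for partners of male patients, so that it matches the contraception period already stated there. If the sponsor prefers to keep 30 days, the protocol should say why the two periods differ.
2. At the Safety Follow-up visit, ask patients of reproductive potential to tell the site of any pregnancy, their own or a partner's, through the end of that period.
3. Ask about pregnancy at the first PD or survival follow-up contact after the period ends, where such a contact occurs.

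Step 3 cannot stand alone. PD follow-up is every 2 months and survival follow-up every 3 months, each ± 1 month, so neither reliably falls at 3 months. PD follow-up also stops when another anticancer therapy starts, while survival follow-up is written as starting after PD. A patient who changes therapy without progression may therefore have neither contact. The instruction in step 2 covers that case.

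**Cost.** A short amendment to Section 10.9, an instruction at an existing visit and one question at an existing contact. The downside is a few extra reports and some follow-up of partners who are not trial participants. No analysis changes.

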# 11. STATISTICAL METHODS

# 11.1. Statistical Analysis Plan

A formal detailed Statistical Analysis Plan (SAP) will be used for the evaluation of the Dose Optimization Phase and Expansion Phase. The SAP will be finalized prior to database lock.

Deviations from the statistical analyses outlined in this protocol will be indicated in the SAP; any further modifications will be noted in the final clinical study report.

# **11.2.** Determination of Sample Size

Approximately 20 patients will be enrolled in the Dose Optimization Phase, with approximately 10 evaluable patients per cohort. However, enrollment may discontinue in either cohort if no CR/PR is noted in the first 5 evaluable patients per cohort. This stopping rule is based on the first stage decision rule of a Simon 2-stage design, with assumptions of a hypothesized ORR of 50% and a null rate of 15% with a one-sided alpha of 0.05 and a power of 85%.

Patients in the Dose Optimization Phase who discontinue before receiving at least 1 cycle of study drug may be replaced.

In the Expansion Phase, the target enrollment is approximately 100 patients with a centrally confirmed diagnosis of PTCL. It is anticipated up to 5% of patients may have a diagnosis that is not confirmed upon central pathology review. One-hundred patients will provide 99.2% power to distinguish between a null ORR of 20% and an alternative ORR of 40% with a two-sided alpha of 0.05. Further, with approximately 100 patients treated at the optimal duvelisib dose, the obtained ORR will have 95% confidence bounds of no greater than  $\pm$  10% when the normal approximation method is employed (assumes 50% ORR). If the observed ORR is greater or less than 50%, the confidence bounds will be less than  $\pm$  10%. These bounds around the obtained ORR are thought to adequately characterize the effect of the optimal dose of duvelisib in this PTCL population.

With protocol amendment 7.0, 20-30 additional patients will be enrolled in the expansion phase. Assuming a total of 120 or 130 patients the power to distinguish between a null hypothesis of ORR of 20% and an alternative ORR of 40% will be 99.4% or 99.6%, respectively. Table 12 has been updated with the 95% confidence bounds using the normal approximation method under the assumption of 120 and 130 total patients.

Table 12 below shows the 95% confidence bounds that would be observed under different ORRs by total number of patients:

ORR %	95% CI Bound	95% CI Bound	95% CI Bound
	(N=100)	(N=120)	(N=130)
30%	21%-39%	22%-38%	22%-38%
35%	26%-44%	26%-44%	27%-44%
40%	30%-50%	31%-49%	32%-48%
45%	35%-55%	36%-54%	37%-54%
50%	40%-60%	41%-59%	41%-59%

#### Table 12: Confidence Bounds for Potential ORR Scenarios

Abbreviations: CI = confidence interval; ORR = overall response rate

The primary analysis for the Expansion Phase will be performed once approximately 100 patients with a centrally confirmed diagnosis of PTCL have been enrolled and evaluated for the primary endpoint. In the event that enrollment in the expansion phase exceeds 110% of the planned sample size, a sensitivity analysis will be performed on the first 100 patients enrolled in the Expansion Phase.

The final analysis for the Expansion phase will be performed once all patients with a centrally confirmed diagnosis of PTCL have been enrolled and evaluated for the primary endpoint. The total number of patients (up to 130) will be determined by the Sponsor. An important driver of the final sample size may be the number of additional patients needed to add an additional 8-10 patients having PTCL subtype of either ALCL or NK cell.

#### **11.3.** Randomization and Stratification

In the Dose Optimization Phase only, patients will be randomly assigned on C1D1 to either Cohort 1 or 2 on a 1:1 basis via a computer-generated randomization scheme. No stratification methodology will be employed in this study.

#### **11.4.** Populations for Analysis

The populations used for analysis will include the following:

- Dose Optimization Efficacy Population, consisting of all patients who 1) receive at least one dose of study drug and 2) complete at least one cycle of treatment and 3) have at least one scan to assess disease response after completion of one cycle of treatment
- The Safety Population, consisting of all patients receiving at least 1 dose of duvelisib

• The mITT Population, consisting of all patients who receive at least one dose of duvelisib which will be used for the Expansion Phase primary and secondary analyses as well as all safety analyses

All patients enrolled into the study will be included in data listings. All primary and secondary analyses will be performed separately for patients in the Dose Optimization and Expansion phases. Additional analyses combining patients from the Dose Optimization and Expansion phases may be performed as applicable. Further details will be provided in the SAP. Summary statistics will be produced by dose level, for patients with dose changes and for the overall study population for both safety and biological effect parameters.

# 11.5. Procedures for Handling Missing, Unused, and Spurious Data

All available efficacy and safety data will be included in data listings and tabulations. Data that are potentially spurious or erroneous will be examined according to standard data management operating procedures.

In general, missing data will be treated as missing and no data imputation will be applied, unless otherwise specified.

#### **11.6.** Patient Disposition

The number of screened patients, screen failures, treated patients, patients who completed the study, and patients who discontinued the study will be summarized. Reasons for discontinuation will also be summarized.

#### 11.7. Demographic and Baseline Characteristics

Demographic and baseline characteristics will be summarized in a descriptive fashion. Data to be tabulated will include gender, age, race, ethnicity, height, and weight, as well as disease-specific characteristics and other parameters as appropriate. These analyses will be conducted on the Safety Population.

# 11.8. Exposure

Treatment exposure will be summarized by cycle and overall.

#### **11.9.** Efficacy Analyses

For the Dose Optimization Phase, all primary and secondary efficacy analyses will be performed using the Dose Optimization Efficacy Population and will be based on the Investigator's determination of response, with the IRC's determination of response used for supportive efficacy analyses. Analysis of the Expansion Phase primary and secondary efficacy analyses will be performed using the mITT population and will be based on the IRC's determination of response, with the Investigator's determination of response used for supportive efficacy analyses. All time to event analyses will present median times to event and 2-sided 95% confidence bounds. Censoring rules will be detailed in the SAP. Neither IRC or Investigator's determination will require confirmation by a second assessment.

Primary Efficacy Analysis:

• ORR will be tabulated using response determination by the Investigator (Dose Optimization) or IRC (Expansion). Best overall response and response assessments over time will be presented along with 2-sided confidence intervals

